4. STUDY DESIGN

4.1. Primary and Secondary Outcomes

According to the aim and objectives of this study, safety and efficacy of Polyoxidonium®, lyophilizate for solution for injections and topical application, 6 mg (NPO Petrovax Pharm LLC, Russia) will be evaluated in hospitalized patients with coronavirus disease (COVID-19).

Efficacy outcomes

Primary efficacy outcome

Subject clinical status using the WHO 7-point ordinal scale on day 15 as compared to baseline.

1. Not hospitalized, no limitations on activities.
2. Not hospitalized, limitation on activities.
3. Hospitalized, not requiring supplemental oxygen.
4. Hospitalized, requiring supplemental oxygen.
5. Hospitalized, on non-invasive ventilation or high flow oxygen devices.
6. Hospitalized, on invasive mechanical ventilation or ECMO.
7. Death.

Secondary efficacy outcomes

Clinical severity assessed by scales

1. Subject clinical status using the WHO 7-point ordinal scale

- Time to improvement of each parameter of the primary scale from admission.

- Subject clinical status at days 3, 5, 8, 11, and 29.
 - Average change in the clinical status at days 3, 5, 8, 11, 15, and 29 as compared to baseline.
2. *The NEWS Score (National Early Warning Score) describes the vital signs (pulse rate, breathing rate, temperature, blood pressure etc.) and its deviation from the reference ranges):* is evaluated daily and on day 15.
- The time to discharge or to a NEWS of ≤ 2 and maintained for 24 hours, whichever occurs first.
 - Change from baseline to days 3, 5, 8, 11, 15, and 29 in NEWS.
3. *Oxygenation, including mechanical ventilation:*
- Change (day by day) in the need for oxygenation in the first 28 days (up to day 29).
4. *Hospitalization*
- Duration of hospitalization (days).
5. *Mortality (date, cause)*
- 28-day mortality.
6. *SOFA scale (evaluation of organ failure associated with sepsis):* is evaluated daily and on day 15.
- Change from baseline to days 3, 5, 8, 11, 15, and 29 in SOFA.

Safety outcomes

Safety outcomes

- Cumulative incidence of serious adverse events/reactions (SAEs, SARs)
- Cumulative incidence of adverse events/reaction (AEs, ARs)
- Permanent or temporary discontinuation of infusions/injections (by any cause)
- Clinically significant changes in the levels of leukocytes, haemoglobin, platelets, creatinine, glucose, total bilirubin, ALT, AST, CRP, and other parameters.

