6.2. Description of the visits

A comprehensive description of visits (by days) is provided in Appendix 1. All procedures described below should be carried out as part of the routine practice of the health care institution.

Preliminary evaluation of the inclusion/exclusion criteria

(Before the study initiation)

Full list of the procedures is provided in Appendix 1.

- Signing of informed consent.
- Confirmation of the positive test for SARS-CoV-2¹.
- Collection of patient history, demographics, and anthropometric data.
- Collection of information about previous/concomitant treatments.
- Physical examination (including lung auscultation).
- Evaluation of chest X-ray or CT scans².
- Laboratory test³: haematology, biochemistry, urinalysis.
- Oxygen saturation (SpO₂).
- Evaluation of the eligibility.

Treatment period

Day 1 - enrolment, initiation of the treatment

Full list of the procedures is provided in Appendix 1.

- Evaluation of measures of clinical support.
- Assessment of the clinical status according to the 7-point ordinal scale.
- Assessment of the clinical status according to the NEWS scale and SOFA scale.
- Oropharyngeal/nasal (OP/N) sample.
- Haematology (only if this test was not performed at the screening).
- Blood chemistry (only if this test was not performed at the screening).
- Urinalysis (only if this test was not performed at the screening).
- Administration of the investigational product
- Physical examination (including lung auscultation).
- Collection of the efficacy data (oxygenation, mechanical ventilation, prolongation of

¹ Data obtained not later than 48 hours before signing the informed consent may be used.

² Recent chest X-ray/CT scans can be used, if the scans were obtained after the coronavirus disease (COVID-19) was diagnosed.

³ If the patient has results of laboratory tests that were performed within 48 before the enrolment, these results can be used to assess the clinical status and eligibility. These data can be used only if they are complete and include all parameters specified in the Protocol. Repeated laboratory tests on Visit 0 are not required in this case.

hospitalization).

- Recording of AEs.

Days 2...18

Full list of the procedures is provided in Appendix 1.

The visits are performed in the in-patient settings. If the patient is discharged before Day 17, the procedures will be performed at the outpatient visits to the clinic.

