Visits to the clinic are preferred after discharge, but the quarantine or other reasonable factors can limit this opportunity. The visits could be performed in a form of phone call or with other remote communication technologies. Some data will not be collected by obvious reasons.

- Evaluation of the measures of clinical support.
- Assessment of the clinical status according to the 7-point ordinal scale — every day during hospitalization up to and including Day 17.
- Assessment of the clinical status according to the NEWS scale and SOFA scale.
- Oropharyngeal/nasal (OP/N) sample.
- Haematology.
- Blood chemistry.
- Urinalysis.
- Administration of the investigational product.
- Physical examination (including lung auscultation).
- Collection of the efficacy data (oxygenation, mechanical ventilation, prolongation of hospitalization).
- Collection of information about concomitant treatments.
- Recording of AEs.

Follow-up period

(Day 29±3)

Full list of the procedures is provided in Appendix 1.

The visits are performed in the in-patient settings. If the patient is discharged earlier, the procedures will be performed within the outpatient visits to the clinic (if possible).

- Evaluation of the measures of clinical support — only if the hospitalization is prolonged.
- Assessment of the clinical status according to the 7-point ordinal scale.
- Assessment of the clinical status according to the NEWS scale and SOFA scale.
- Oropharyngeal/nasal (OP/N) sample.
- Haematology.
- Blood chemistry.
- Urinalysis.
- Collection of the efficacy data (oxygenation, mechanical ventilation, prolongation of hospitalization).
- Collection of information about concomitant treatments.
- Physical examination (including lung auscultation).
- Recording of AEs.

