9.7.2.2. Analysis of the secondary efficacy endpoints

The interval (quantitative) data will be described with arithmetic mean, standard deviation, median, lower quartile (25%) and higher quartile (75%), minimum, maximum, coefficient of variation, and 95% confidence interval for the mean. The categorical (qualitative) data will be described with incidences, percentage, or proportions, and 95% confidence interval for percentage or proportions.

The time to event data will be processed via survival analysis with the use of Kaplan-Meier curves and 95% confidence intervals.

The following standard parametric tests are planned for comparison of quantitative data with normal distribution: Student t-test for dependent/independent samples, analysis of variance (ANOVA) for repeated measurements.

The following standard non-parametric tests are planned for comparison of quantitative data with distribution other than normal: Mann-Whitney U-test, Wilcoxon T-test, Friedman test.

Shapiro-Wilk test will be used to test normality of the distribution.

The incidences will be compared between the treatment groups with Pearson's χ^2 -test or Fischer's exact test.

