16. APPENDICES

SCHEDULE OF ASSESSMENTS

Table 1. Study plan
(ALL THESE PROCEDURES SHOULD BE CARRIED OUT IN THE FRAMEWORK OF ROUTINE PRACTICE OF THE HEALTH CARE INSTITUTIONS)

Procedure / days	Study according to the Protocol No. COVID dated March 30, 2020				
	Day 1	Daily (up to discharge ^{***})	Day 3, 5, 7, 11	Day 15±1	Day 29±3 or any other last day ^{****} of the study
Enrolment criteria	X				
Withdrawal criteria		X	X	X	X
Informed consent, enrolment	X				
Polyoxidonium	10 doses: days 1, 2, 3, 5, 7, 9, 11, 13, 15, 17				
History	X				
Clinical signs and symptoms, physical examination¹	X	X	X	X	X
Nasopharyngeal and/or oropharyngeal smear	X		X	X	X
Haematology²	X**		X	X	X
Blood chemistry³	X**		X	X	X
CRP	X**		X	X	X
Urinalysis⁴	X**		X	X	X
Bacteriological inoculation of sputum	If necessary				
Chest X-ray/ CT*	If indicated				
ECG*	If indicated				
SpO₂⁵	X	X	X	X	X
Evaluation of need for oxygenation, including mechanical ventilation	X	X	X	X	X
Assessment of the treatment efficacy⁶	X	X	X	X	X
Assessment of safety	X	X	X	X	X
NEWS Score	X	X	X	X	X
SOFA Score	X	X	X	X	X
Clinical status by WHO scale	At admission	X	X	X	X

Notes to Table 1

*- including at admission, before enrolment

** - results of the previous laboratory investigations within 48 hours before enrolment can be used

*** - visits to the clinic are preferred after discharge, but the quarantine or other reasonable factors can limit this opportunity. The visits could be performed in a form of phone call or with other remote communication technologies. Some data will not be collected by obvious reasons.

**** - in case of the patient withdrawal (see the withdrawal criteria)

1 – Clinical signs and symptoms

Weakness, fatigue, cough, shortness of breath, stuffiness in the chest, myalgia, headaches, haemoptysis, palpitations, nasopharyngeal symptoms, diarrhoea, nausea, vomiting; physical

examination: heart rate, blood pressure, respiratory rate, body temperature

2 – Haematology

Red blood cells, haematocrit, white blood cells, platelets, neutrophils, eosinophils, basophils, monocytes, lymphocytes

3 - Blood chemistry

Urea, creatinine, Na⁺, K⁺, bilirubin, glucose, ALT, AST, albumin, pH, bicarbonates, lactate, coagulogram with prothrombin time, coagulogram with international normalized ratio and activated partial thromboplastin time, CRP

If indicated: PaO₂, FiO₂, PaCO₂

4 – Urinalysis

According to routine practice of the centre

5 - SpO₂

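### Return to unrestricted activity (category 1 of the WHO scale) has no event-date or interval-censoring rule, and no assessment day is named between Day 15–18 and Day 29±3.

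*Combined protocol and SAP*

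**What the plan says.** - **Endpoint.** Section 4.1 lists as a secondary outcome "Time to improvement of each parameter of the primary scale from admission". It does not define improvement further. I read it as covering each step of the scale, including category 1, "Not hospitalized, no limitations on activities".
- **Method.** Sections 9.1 and 9.7.2.2 both state: "The time to event data will be processed via survival analysis with the use of Kaplan-Meier curves and 95% confidence intervals". No other time-to-event method is named. Neither section says which date counts as the event when a status is first seen at a contact.
- **Schedule, Table 1 (Section 16).** The WHO scale is marked in the daily column, headed "Daily (up to discharge", and at Days 3, 5, 7, 11, at Day 15±1, and at "Day 29±3 or any other last day". Doses are listed on Days 1, 2, 3, 5, 7, 9, 11, 13, 15 and 17.
- **Schedule, Section 6.2.** In the block for Days 2 to 18 the scale is scored "every day during hospitalization up to and including Day 17". The same block says "If the patient is discharged before Day 17, the procedures will be performed at the outpatient visits to the clinic", allows phone or other remote contact, and does not list the days. The only assessment listed for the follow-up period is Day 29±3.
- **Event date.** No field or procedure asks when the patient resumed usual activities.

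**The concern.** Category 1 requires the patient to be out of hospital, which is where scoring becomes sparse. A recovery between two contacts is known only to lie in that interval. Ordinary Kaplan-Meier needs a single date, and the only one the plan is sure to produce is the contact date. (Section 6.3.8 assigns a scale score to the day before it is obtained, which moves this by one day at most.) Dating at the contact always errs late. The error is largest in the longest interval, which is the last one, so it falls mainly on slower recoveries.

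The study has no comparator, so the curve and its median are the reported result for this endpoint. If a large share of events falls at the final visit, the visit calendar partly determines the median, and the planned 95% interval does not reflect that uncertainty.

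**Working it through.** The plan gives no figure for this endpoint to reproduce. The only design number is a sample of at least 50 patients in one group.

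**Step 1: the gap, on three readings of the post-discharge schedule (nominal days)**

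- A, the Table 1 columns (3, 5, 7, 11, 15, 29): 29 − 15 = 14 days.
- B, A plus dosing Days 9, 13 and 17 as contacts: 29 − 17 = 12 days.
- C, daily contacts to Day 18 under the Section 6.2 block, then Day 29: 29 − 18 = 11 days.

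With the visit windows, the interval from the Day 15 visit to the last visit runs from 26 − 16 = 10 days to 32 − 14 = 18 days.

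**Step 2: delay if the contact day is the event day**

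For a gap of g days with recovery equally likely on each day up to and including the contact, the delay takes the values 0, 1, …, g − 1, with mean (g − 1)/2.

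- Last gap: A, 13/2 = 6.5 days; B, 11/2 = 5.5 days; C, 10/2 = 5.0 days.
- Before Day 15 the longest gap on A is 4 days (7 to 11, 11 to 15): mean 3/2 = 1.5 days, maximum 3 days.

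**Step 3: effect on the curve**

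This needs discharge and recovery times, which the documents do not give. Assumptions: discharge lognormal with median 8, 12 or 16 days and log-SD 0.4; lag from discharge to category 1 exponential with mean 3, 7 or 10 days; no deaths or dropout; last visit exactly on Day 29. There were 200,000 simulated patients per scenario. Mean delay is among events seen by Day 29.

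| Discharge median / mean lag | True median | Reported median A / B / C | Dated Day 29, % of patients A / B / C | Truly on Day 29, % | Mean delay, days A / B / C |
|---|---|---|---|---|---|
| 8 / 3 | 12 | 15 / 13 / 12 | 23 / 14 / 10 | 0.2 | 3.3 / 1.5 / 0.8 |
| 8 / 7 | 15 | 15 / 15 / 15 | 40 / 29 / 25 | 1.1 | 4.4 / 2.5 / 1.7 |
| 8 / 10 | 17 | 29 / 17 / 17 | 43 / 33 / 29 | 1.6 | 4.6 / 2.8 / 2.0 |
| 12 / 3 | 16 | 29 / 17 / 16 | 49 / 36 / 30 | 0.9 | 5.1 / 3.0 / 2.1 |
| 12 / 7 | 19 | 29 / 29 / 29 | 56 / 45 / 39 | 2.1 | 5.5 / 3.6 / 2.7 |
| 12 / 10 | 22 | 29 / 29 / 29 | 52 / 43 / 39 | 2.4 | 5.5 / 3.8 / 2.9 |
| 16 / 3 | 20 | 29 / 29 / 29 | 63 / 51 / 45 | 2.3 | 5.9 / 4.1 / 3.1 |
| 16 / 7 | 24 | 29 / 29 / 29 | 58 / 50 / 45 | 3.1 | 5.7 / 4.2 / 3.4 |
| 16 / 10 | 26 | 29 / 29 / 29 | 51 / 45 / 41 | 3.1 | 5.6 / 4.2 / 3.5 |

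Across scenarios and readings, 10–63% of patients have the event dated Day 29. With 50 patients that is 0.10 × 50 = 5 to 0.63 × 50 ≈ 32. When the true median is no later than the last contact before the gap, the reported median moves little or not at all. When it falls inside the gap, the reported median is Day 29. A true median of 16 becomes 29 on A but 17 on B and 16 on C; a true median of 19 or later becomes 29 on all three.

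**The case against.** The strongest reply is that the schedule is less sparse than the Table 1 columns suggest. Section 6.2 places procedures for early-discharged patients at outpatient visits or remote contacts within Days 2 to 18. Doses fall on Days 9, 13 and 17. The ±1 and ±3 windows make Days 16 and 26–28 valid, and Section 6.1 allows additional visits. A reader might infer from Table 1 that a discharged patient is scored only at its listed days and that nothing can be recorded on Days 16–28. The documents do not support that. This reply reduces the size, as readings B and C show, but the last nominal gap is still 11 days at its shortest.

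Second, no sentence makes the detection day the event day. That is the default where no rule is given. Sections 9.3 and 9.7 allow methods to be replaced or added, so interval censoring is not excluded. This stands as a correction of wording: the defect is a missing rule, not a wrong one. Permission to change methods later does not specify one in advance.

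Third, recovery may be fast. Section 9.7.2.1 gives as an example that all mild patients may have resumed normal activities by Day 15. For them the delay is at most 3 days, so a cluster at the last visit is not inevitable.

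Fourth, the reach is narrow. Changes in oxygen support, ventilation and discharge can be dated from hospital records. Only category 1, one component of one secondary endpoint, is materially affected.

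**Conclusion.** The point holds as a limited one. The plan names ordinary Kaplan-Meier, gives no event-date or interval-censoring rule for a status reached after discharge, and names no assessment day between Day 15–18 and Day 29±3. By default, recoveries in that gap are dated at the last visit (Days 26–32), on average 5.0–6.5 days late if they are uniform within the gap. The late direction does not depend on assumptions. The size does: the 10–63% share at Day 29 and any shift in the median rest on the assumed discharge and recovery times and on the reading of the schedule.

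It would be tempting to conclude that the whole time-to-improvement analysis is set by the visit calendar, or that a treatment comparison is biased. Neither follows. In-hospital steps can be dated, and there is one arm, so what is affected is a descriptive curve and its median. In-hospital scoring is not uniformly daily on paper either: Section 6.2 stops it at Day 17, while Table 1 continues it to discharge.

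**What to change.** 1. **Main remedy.** Add one eCRF field at each existing post-discharge contact, including phone contacts, for the date on which usual activities were resumed without limitation. Use that date as the event date for category 1.
2. **Analysis text, Sections 9.1 and 9.7.2.2.** State that, where no such date is available, time to category 1 will be treated as interval-censored between the last contact without the status and the first contact with it, using the Turnbull estimator. Add that this shows the uncertainty in the last gap but cannot locate events within it.
3. **Reconcile Table 1 with Section 6.2.** State on which days the scale is scored after discharge, and whether daily in-hospital scoring ends at Day 17 or at discharge.

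Cost: one date field, one analysis sentence and one schedule clarification, issued as a written amendment under Section 11.7. No new visit is needed. The downsides are small: recalled dates carry some error, and the interval-censored curve will be wider.

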9.4. Drop-outs, withdrawn patients, and missing data

No missing data will be substituted. The missing/omitted data will not be considered during statistical analysis.

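### If the named across-time tests are run on NEWS and SOFA, one missing visit or a death removes all of that patient's observed values from the Friedman test and from classical repeated-measures ANOVA.

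*Combined protocol and SAP*

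**What the plan says.** Section 9.7.2.2, like 9.1 and the synopsis, gives a general list of tests. For normally distributed quantitative data it names the Student t-test (dependent or independent samples) and "analysis of variance (ANOVA) for repeated measurements". For other distributions it names "Mann-Whitney U-test, Wilcoxon T-test, Friedman test". Shapiro-Wilk decides between the two lists. No endpoint is assigned to a particular test.

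The endpoints in 4.1 are "Change from baseline to days 3, 5, 8, 11, 15, and 29 in NEWS", "Change from baseline to days 3, 5, 8, 11, 15, and 29 in SOFA" and, for the 7-point WHO scale, "Average change in the clinical status at days 3, 5, 8, 11, 15, and 29 as compared to baseline".

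On missing data, 9.4 says only: "No missing data will be substituted. The missing/omitted data will not be considered during statistical analysis". There is no rule for incomplete rows and no NEWS or SOFA value after death. On the WHO scale, death is category 7.

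The plan expects gaps. After discharge clinic visits are preferred, but under 6.2 "The visits could be performed in a form of phone call or with other remote communication technologies", and both 6.2 and the notes to Table 1 accept that some data will then not be collected.

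Section 9.7.2 makes ITT (all enrolled patients, 9.6) the main efficacy population. Section 11.8 lists a missed visit as an example of a significant deviation and removes patients with such deviations from the final efficacy analysis.

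**The concern.** This is a single-group study (4.2), so inference on change over time must come from within-patient tests. The two named tests that compare several days at once normally work on complete rows. A patient measured in hospital on Days 3, 5, 8, 11 and 15 but reached only by phone on Day 29 would contribute nothing to such a test, although most of the row was observed.

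The patients lost this way are not a random subset. NEWS needs respiratory rate, saturation, temperature, blood pressure and pulse (6.3.8), which a phone call will generally not supply. Table 1 schedules Day 7 rather than the Day 8 used by the endpoints, so Day 8 rests on daily assessment up to discharge or on the general provision for outpatient visits in 6.2. Patients who die have no later NEWS or SOFA. An across-time test on complete rows therefore tends to describe those who neither left early nor died, in a study that sets at least 50 patients and replaces nobody who withdraws (5.5).

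**Working it through.** The plan states no figure for complete rows, missing visits or deaths, so there is nothing of its own to reproduce. The rates below are assumptions.

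**1. Length of a complete row.** Baseline plus Days 3, 5, 8, 11, 15 and 29 = 7 values, of which 6 are post-baseline.

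**2. What the tests do with a gap.** Simulated data: 50 patients, 7 time points, 10 patients lacking only the last value. Observed values: 50 × 7 − 10 = 340. Values in complete rows: 40 × 7 = 280. Observed values at risk: 340 − 280 = 60.

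| Method | What was used |
|---|---|
| R friedman.test | Statistic 133.44 on the full data and 133.44 on the 40 complete patients, so the other 10 were dropped |
| scipy Friedman, missing values omitted (separate simulated set) | 133.20, the same as complete cases only |
| R multivariate linear model | 40 patients |
| statsmodels AnovaRM | Refused the unbalanced data; ran on the 40 |
| R aov with a patient error stratum, long data | Kept incomplete patients: residual df 340 − 50 − 6 = 284, against 280 − 40 − 6 = 234 |
| Likelihood-based mixed model | 50 patients, 340 values |

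The Friedman test loses the 60 values in either package. For ANOVA the result depends on the implementation, and 9.2 allows R, SAS or other software without specifying one.

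**3. Patients remaining.** Let q be the share missing at each post-baseline visit, independent across visits. Complete rows = 50 × (1 − q)^6. Share of observed post-baseline values discarded = 1 − (1 − q)^5.

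| q | (1 − q)^6 | Patients of 50 | Observed values discarded |
|---|---|---|---|
| 2% | 0.886 | 44.3 | 9.6% |
| 5% | 0.735 | 36.8 | 22.6% |
| 10% | 0.531 | 26.6 | 41.0% |

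**4. Deaths (NEWS and SOFA only).** With a share d dying before Day 29, complete rows = 50 × (1 − d) × (1 − q)^6. At d = 10%: 45.0 with q = 0, 33.1 with q = 5%, 23.9 with q = 10%.

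**5. Clustering.** Independence is the pessimistic end. If the same 10% of patients miss every visit, 50 × 0.90 = 45 remain rather than 27. Discharge and death do cluster gaps in the same patients, so the truth should lie between these figures for a given q.

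**6. Direction of bias, deaths alone.** Assume an early mean NEWS change of −1 in survivors and +1 in those who later die. With 10% deaths, all patients average 0.9 × (−1) + 0.1 × 1 = −0.8, while complete rows average −1.0. Losing fast recoverers pulls the other way, so the net direction cannot be determined from the documents.

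**The case against.** The strongest reply is that 9.7.2.2 is a menu. It also names the paired t-test and the Wilcoxon test, which suit endpoints worded as change from baseline to a given day. Each needs two values, so a patient without Day 29 stays in the Day 3 and Day 5 comparisons, and the per-visit summaries with confidence intervals use whatever was observed. This stands. A reader might infer that an incomplete patient leaves the whole efficacy analysis. The listed tests do not imply that; only the across-time tests are affected, and only if they are run.

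A reader might also infer that both named methods always require a full row. They do not: one common R form of repeated-measures ANOVA keeps incomplete patients. That leaves the number analysed to an unstated software choice, and it does not help the Friedman test.

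It is also tempting to say that the WHO-scale results exclude deaths and fast recoverers. The documents do not support this. Death has a category, and status after discharge (categories 1 and 2) can plausibly be obtained by phone. What is missing is a statement that 7 is carried to all later days. Even for NEWS and SOFA, fast recoverers are not necessarily lost, because clinic visits are preferred.

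Sections 9.3 and 9.7 allow methods to be replaced or added, but they name no alternative and leave the decision until after data collection.

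**Conclusion.** The concern holds in a limited form. If an across-time test is run on NEWS or SOFA, the Friedman test, and repeated-measures ANOVA in its classical form, use only complete seven-value rows, and 9.4 permits nothing to fill a gap. That sits badly with ITT as the main efficacy population. Paired tests and per-visit summaries are unaffected unless the 11.8 exclusion is applied, in which case those patients are lost there too. The WHO scale is affected much less.

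The size is unknown. The figures of about 44, 37 and 27 of 50 rest on assumed, independent rates of 2%, 5% and 10%, and clustering would leave more. These are secondary endpoints, but the loss is foreseeable and cheap to avoid, so the plan should be changed.

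**What to change.** In 9.1 and 9.7.2.2, and in the matching synopsis text:

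- For NEWS and SOFA, replace the omnibus repeated-measures ANOVA and Friedman test with a likelihood-based mixed model on all observed values, with visit as a category and baseline score and severity as covariates. State that the estimates are meant to describe patients while alive, and report the number of deaths beside each visit.
- For the WHO scale, use a cumulative-logit mixed model with death carried as 7 on all later days. Unweighted GEE is not a good substitute, because it generally needs data missing completely at random.
- Reconcile the exclusion in 11.8 of patients who missed a visit with ITT in 9.7.2. If the exclusion stays, the model will not recover those patients.

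The cost is SAP wording and slightly more programming. The models assume that gaps are missing at random given the observed data. A mixed model for NEWS and SOFA also implicitly projects scores beyond death; reporting deaths beside each visit makes this visible but does not remove it.
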